2.1.1 Hypotheses

- PHARM and PEER will achieve similar improvements in older adults' knowledge of vaccine preventable diseases (primary hypothesis)
- PHARM and PEER will improved beliefs about vaccinepreventable disease
- 3) **PEER will be a lower cost approach** to educating participants in the senior center compared to PHARM
- 4) PHARM and PEER will result in similar rates of participants taking one or more activation step(s) to obtain vaccination
- 5) Participants will be highly satisfied with the PHARM and PEER interventions

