TITLE: Randomized Trial of Peer-to-Peer Versus Pharmacist Education to

Improve Older Adults' Vaccination Knowledge Through the Senior Center Model of Care

CLINICALTRIALS.GOV

NCT NUMBER

NCT03239665

March 6, 2020 **DOCUMENT DATE:**

Overview of Statistical Analysis

The design of the study was a randomized trial with randomization to PHARM or PEER performed at the program date level. The primary outcome measure was a between-group comparison of change in knowledge for PHARM vs. PEER at BL vs. PT, and BL vs. M1. Secondary measures included between-group examinations of beliefs, trust, and activation at all 3 time points (BL vs. PT and M1). We also measured within-group differences in knowledge, beliefs, and activation and the intervention costs of PHARM and PEER, including program development, training and implementation.

Study data was recorded using paper forms and input into SAS Version 9.4 for analysis. Electronic data was password-protected by CIP while enrollment and data collection were ongoing. Files were checked to ensure de-identification prior to sharing with the Rutgers University investigators who completed the analyses.

Analysis was performed using an Intention-to-Treat (ITT) sample. This sample included all participants meeting study including criteria with ≥ 1 documented response from the baseline survey. In the case of missing data from the post-intervention or one-month follow-up survey, the matrix below was used to carry forward observations. For all tests, the significance level was chosen as $\alpha = 0.05$, and was downward adjusted via the Bonferroni method when appropriate.

Table 1. ITT approach for handling missing follow-up data.

BL Data	PT Data	M1 Data
Present	Present	Absent Utilize PT Data
Present	Absent	Present
	Utilize BL Data	
Present	Absent	Absent
	Utilize BL Data	Utilize BL Data

^{*}BL = baseline, PT = post-intervention, M1 = one-month follow-up

Baseline Demographics

Demographic analysis was carried out via t-test for continuous variables and Chi-square test for categorical variables.

Knowledge

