The number of correct responses to the knowledge items at each timepoint was calculated as a whole and by disease (pneumonia, influenza, zoster). Baseline knowledge was compared by race via Kruskal-Wallis test. Because the knowledge data were expected to be non-normal and integer-valued, knowledge items were assessed using nonparametric methods. Specifically, between-group differences in knowledge were assessed at each timepoint via Wilcoxon Rank-Sum test. Similarly, between-group knowledge differences across timepoints were assessed pairwise via Wilcoxon Rank-Sum tests with Bonferroni-corrected significance threshold of

 α =0.05/3=0.0167. Within-group differences in knowledge score across timepoints were tested pairwise using Wilcoxon Signed-Rank tests.

Beliefs

The percentage of respondents answering "Completely Agree" to each item at each timepoint was calculated and compared between PHARM and PEER, as in our PPPP study. Pairwise Wilcoxon Signed-Rank tests were run comparing within-group changes in beliefs across timepoints applying Bonferroni correction (α =0.05/3=0.0167). Either Chi-Square or Fisher's Exact tests were used to compare beliefs between groups at each timepoint, depending on expected cell counts.

Activation

For all participants, Chi-Square or Fisher's Exact testing was performed as appropriate at each timepoint to assess between-group differences in proportions of participants planning actions, including planning vaccination and planning to speak with a doctor, pharmacist, or family/friends, as well as actions taken, including vaccinations obtained and having spoken with a doctor, pharmacist, or family/friends.

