For participants who did not report positive vaccination status on the post-intervention survey, Chi-Square or Fisher's Exact testing was performed on PT & M1 data for each vaccine type to test for differences between PHARM and PEER with significance level α =0.05. The PT response to the vaccination items was chosen instead of the BL response because it was felt that the responses to these items would be more reliable and accurate after having received the intervention as compared to baseline, when participants may have had a less clear ability to differentiate between the vaccines they may have received. For survey items pertaining to plans/actions related to vaccines, participants not reporting positive vaccination status were compared between PHARM and PEER at each timepoint for item (discussion with doctor, pharmacist, or family/friends) via Chi-Square or Fisher's Exact tests as appropriate.

Satisfaction

For both PT and M1, proportions of respondents answering favorably ("Completely Agree" or "Somewhat Agree") and unfavorably ("Completely Disagree" or "Somewhat Disagree") to the two satisfaction items (program satisfaction and program engagement) were compared between PHARM and PEER using either Chi-Square or Fisher's Exact test as appropriate.

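### The SAP's Activation section replaces the protocol's single one-month measure for Objective 4 with about 35 to 39 between-arm tests, names no lead test, and leaves the multiplicity adjustment undefined.

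*SAP*

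**What the plan says.** The protocol treats activation as one quantity. Hypothesis 4 (2.1.1) reads "PHARM and PEER will result in similar rates of participants taking one or more activation step(s) to obtain vaccination". Section 2.7.2 (Activation, Objective 4) measures it as the percent of participants reporting one or more steps at one month. Steps include talking to a physician, pharmacist, friends or family, or receiving pneumonia or zoster vaccine. Influenza vaccination is excluded.

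The SAP's Activation section works item by item:

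- **All participants:** tests "at each timepoint to assess between-group differences in proportions of participants planning actions". Four plans are listed: to be vaccinated, and to talk with each of three parties (a doctor, a pharmacist, or people close to the participant). The four matching steps already taken are tested in the same way.
- **Participants without positive vaccination status on the post-intervention survey:** tests on post-test (PT) and one-month (M1) data for each vaccine type, "to test for differences between PHARM and PEER with significance level α =0.05".
- **Participants not reporting positive vaccination status:** tests of discussion with doctor, pharmacist, or family/friends at each timepoint.

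On multiplicity, the SAP Overview says that the 0.05 level "was downward adjusted via the Bonferroni method when appropriate". The SAP then spells out an adjustment in two places: between-group knowledge differences across timepoints, and within-group changes in beliefs ("applying Bonferroni correction (α =0.05/3=0.0167"). The Activation section mentions no adjustment. The Overview calls activation a secondary measure.

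**The concern.** Objective 4 has a defined measure in the protocol but no corresponding test in the SAP. An analyst following the SAP would produce several dozen p-values and no stated rule for which of them answers the objective.

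This matters in both directions. If activation really is similar in the two arms, as Hypothesis 4 predicts, a list this long can easily throw up a nominally significant item, timepoint or subset, and that item could be reported as the activation finding. Equally, non-significant items could be picked out and cited as showing similarity. Because the SAP is written in the past tense and leaves open when Bonferroni applies, the documents do not show that either choice was fixed before the results were seen.

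**Working it through.** **1. The plan's own multiplicity figure.** 0.05/3 = 0.0167. It reproduces, but it is stated for knowledge and within-group beliefs only. The documents give no test count or familywise error for activation.

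**2. Count of between-arm activation tests.** Timepoints are baseline (BL), PT and M1 (SAP Overview). Three vaccine types is an assumption taken from the disease list in the SAP's Knowledge section; the Activation section gives no number.

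| Block | BL | PT | M1 | Total |
|---|---|---|---|---|
| All participants: 4 plans + 4 actions | 8 | 8 | 8 | 24 |
| Vaccine-type tests, not vaccinated at PT | 0 | 0 | 3 | 3 |
| Discussion items, not reporting vaccination | 3 | 3 | 3 | 9 |
| Total | 11 | 11 | 14 | 36 |

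The PT vaccine-type tests are left out here. If the subset is defined separately for each vaccine, everyone in it is unvaccinated at PT and the test is empty.

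Other readings:
- Three types, PT and M1 tested separately: 24 + 6 + 9 = 39.
- Two types (influenza excluded): 24 + 2 + 9 = 35, or 24 + 4 + 9 = 37 with PT tested.
- Plans and actions tested separately in the discussion block: 9 more.

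So the count is about 35 to 39. In the 36-test reading, 36 − 11 = 25 tests are post-baseline and 14 of those are at M1.

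**3. Chance of at least one p < 0.05 if the arms do not differ and no adjustment is made.** For k independent tests it is 1 − 0.95^k:
- k = 25: 1 − 0.95^25 = 0.72
- k = 14: 1 − 0.95^14 = 0.51

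For correlated tests, take normal statistics with a common pairwise correlation ρ. With c = 1.96 and the common factor S standard normal, the chance is 1 − E{[Φ((c − √ρ·S)/√(1−ρ)) − Φ((−c − √ρ·S)/√(1−ρ))]^k}, evaluated numerically. The documents give no correlation, so a range is shown.

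| Tests | ρ = 0 | ρ = 0.3 | ρ = 0.5 | ρ = 0.8 |
|---|---|---|---|---|
| 25 post-baseline | 0.72 | 0.61 | 0.47 | 0.24 |
| 14 at M1 | 0.51 | 0.44 | 0.35 | 0.20 |

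Expected false positives, whatever the correlation: 25 × 0.05 = 1.25 and 14 × 0.05 = 0.7.

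**4. Would borrowing the knowledge threshold help enough?** With 0.05/3 per test and independence, 1 − (1 − 0.05/3)^25 = 0.34 and 1 − (1 − 0.05/3)^14 = 0.21. Both remain well above 0.05.

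**The case against.** The strongest reply is that activation is declared secondary, knowledge is the primary outcome, and strict familywise control over secondary items is often treated as a matter of reporting. The protocol also does define one activation measure, so the trial as a whole is not without a lead. Both points stand, and they narrow the issue. The defect is that the SAP does not carry the protocol's measure forward and does not label what it tests instead.

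A reader might also infer something stronger: that the SAP runs at least 36 tests, each at 0.05, so that a false arm difference is more likely than not. The documents do not support this.
- Thirty-six is not a floor. It needs three vaccine types, and the protocol's exclusion of influenza makes 35 possible.
- An unadjusted 0.05 is written only for the vaccine-type tests. For the others the Overview's conditional Bonferroni clause applies, so the plan is unclear rather than explicit.
- Baseline differences cannot show a program effect, so 11 of the 36 tests do not belong in that probability.
- Without them, the chance passes one half only at lower correlations (0.54 at ρ = 0.4, 0.47 at ρ = 0.5). Shared respondents, overlapping subsets and carried-forward data all make correlation likely.

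Finally, Hypothesis 4 is about similarity, and a two-sided difference test cannot establish that. This is correct. Naming one test cures the selection problem, not the inference from a non-significant result.

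**Conclusion.** The point holds as a should-fix on a secondary objective. Following the SAP as written leaves Objective 4 without its defined comparison and open to selective reporting among about 35 to 39 tests.

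Without adjustment, the chance of some nominally significant difference after baseline is roughly 5 to 14 times the nominal 0.05 (0.24/0.05 to 0.72/0.05). Among the M1 tests alone it is roughly 4 to 10 times (0.20/0.05 to 0.51/0.05). These figures assume no true difference in any item, the 36-test reading, a common correlation between 0 and 0.8, and individually valid tests. They leave out any clustering of responses by program date, the SAP's unit of randomization; positive clustering would inflate the error of each individual-level test further.

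**What to change.** In the SAP's Activation section:

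1. Make the protocol's composite (one or more steps towards pneumonia or zoster vaccination at one month, influenza excluded as the protocol states) the single between-arm comparison for Objective 4. Report it as a difference in proportions with a 95% CI, tested at two-sided 0.05. It should be this measure and no other M1 contrast, because it was stated in the protocol and so is not open to choice after the data are known.
2. State that a non-significant result will not be read as evidence of similarity, and that the confidence interval will be used to show which differences remain compatible with the data.
3. Remove the baseline between-arm activation tests.
4. Report all other activation comparisons (single items, post-test, participants not reporting vaccination) with 95% CIs, labelled exploratory.

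The cost is SAP and manuscript wording, plus deriving one variable from responses already collected. The small downside is that single-item differences can no longer be claimed as confirmatory at 0.05.

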2.7.2 Definitions of Study Measures

Study measures will be assessed at baseline, immediately following the program ("posttest"), and 1 month after the program. The baseline and posttests will be administered in person on the date of the intervention. The 1 month follow up will be administered by phone (with up to 4 attempts to reach the participant). It should be noted that the team considered a more distal follow up point (i.e., at 2 or 3 months), but based on experience with the prior PPPP study felt that an earlier follow up would make it easier to reach participants with fewer call attempts. If the reviewers of this proposal conclude that 1 month is too soon for a follow up, we are willing to revise our plan to include a follow up at 2 or 3 months.

Knowledge and awareness of vaccine-preventable disease (Objective 1):

Knowledge and awareness about the target vaccine-preventable diseases will be assessed with a 15-20 item inventory encompassing the following domains: susceptibility to infection, symptoms of disease, severity of illness, and vaccination with an emphasis on vaccine efficacy, safety, and eligibility. These items will be selected following a review of the literature since no single validated instrument exists to assess knowledge of all three target diseases. ^{28,29,32,33,36-40}

Similar to the prior pneumonia project, **pneumonia knowledge** will be assessed using an instrument developed by our group using previously published literature. The prior instrument consisted of 6 "check all that apply" questions. Each item correctly checked was worth 1 point, for a maximum possible score of 28 points (see Figure 4 for a summary). We plan to retain the same instrument for the proposed study in order to enable comparison of pneumonia knowledge between the studies. However, we will also add a module pertaining to **zoster knowledge** which takes the same form as the established instrument.

Figure 4. Summary of Pneumonia Knowledge Instrument

Knowledge Assessment Questions	Maximum Number of Correct Responses Possible
Who is at risk of getting pneumonia?	9
How can you catch pneumonia from an infected person who is near you?	4
Which of these are symptoms of pneumococcal disease?	5

I should call my doctor or get emergency help if I get any of the following problems after vaccination:	5
Which of the following are possible side effects of the pneumonia vaccine?	5
TOTAL SCORE	28

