Intervention costs for PHARM and PEER will be calculated as the monetary value of time and materials required to train involved personnel, and deliver PHARM and PEER as well as personnel travel costs. Data on personnel time requirements for delivering PHARM and PEER will be collected in real time by

trained staff members using time logs which document the time and staff members required for training and delivery of the program. These data will be monetized using the hourly wage rates plus fringe benefit costs of the involved personnel. Other costs include materials such as signage, a modest participant giveaway such as medication reminder cards and pill box, printing/duplication, and food/refreshments. All costs will be reported in \$US 2017, consistent with the intervention time period.

Activation (Objective 4):

Participant activation will be measured as percent of participants who report taking one or more actions towards receiving vaccination at one month post-intervention, such as discussion with a healthcare provider (physician/pharmacist) or friends/family and/or receiving vaccination for either pneumonia or zoster. For participants who report vaccination, we will report which (pneumonia, zoster, or both). Influenza vaccination activation will be excluded from this measure since influenza vaccination is widely promoted through other initiatives which could influence activation, such as onsite flu shots at CIP.

Satisfaction (Objective 5):

Satisfaction measures will include **participants' overall satisfaction** with the content and delivery of PEER vs PHARM, the extent to which the participant felt **engaged**, and their **satisfaction with information received**. Satisfaction will be measured only at post-test using a simple 5-10 item satisfaction survey adapted from our prior research.

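### Satisfaction is tested at one month although the protocol collects it only at post-test, and the SAP's general carry-forward rule does not fit this outcome

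*SAP*

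**What the plan says.** Protocol section 2.7.2 opens with a general schedule of baseline, post-test and one month for the study measures ("Study measures will be assessed at baseline, immediately following the program"). Its paragraph on Satisfaction (Objective 5) then narrows this for one outcome: "Satisfaction will be measured only at post-test using a simple 5-10 item satisfaction survey adapted from our prior research".

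The Satisfaction section of the SAP differs on timing and on content. It begins "For both PT and M1, proportions of respondents answering favorably" and applies the comparison "to the two satisfaction items (program satisfaction and program engagement) were compared between PHARM and PEER", using chi-square or Fisher's exact tests. It gives no reason for the added time point or for the reduction to two items.

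The missing-data rule is in the SAP's Overview of Statistical Analysis and is worded for the whole analysis: "In the case of missing data from the post-intervention or one-month follow-up survey, the matrix below was used to carry forward observations". Table 1 fills an absent M1 value from PT ("Absent Utilize PT Data") and an absent PT value from baseline ("Utilize BL Data"). If both follow-ups are absent, both are filled from baseline. The analysis sample is every eligible participant "with ≥ 1 documented response from the baseline survey", so a post-test answer is not needed for entry. Neither the Overview nor the Satisfaction section exempts satisfaction from the table.

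**The concern.** Two things do not fit together. First, the SAP tests an outcome at a time when, according to the protocol, it was not collected. Where the two disagree, the reader cannot tell what data the M1 test contains. Second, carry-forward assumes that the earlier value measures the same thing as the missing later one. A PT rating is given in person on the day of the session and is not a one-month rating. A baseline rating of a program that the participant has not yet attended does not exist.

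What is at stake is the reading of Objective 5 and its hypothesis that participants will be highly satisfied. An M1 result for satisfaction looks like a second, later observation. Depending on what was collected, it may hold no new information, or a mixture of one-month and same-day answers in proportions that the SAP does not report.

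**Working it through.** Neither document states a figure for this point, so there is none to reproduce. The check applies Table 1 to a satisfaction item under each possible collection schedule.

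**Inputs**
- Collection: PT only (Protocol 2.7.2, Satisfaction) or PT and M1 (implied by SAP, Satisfaction).
- Fill rule: M1 from PT; PT from baseline (SAP, Table 1).
- Planned size: 158 per arm (Protocol 2.7.3).
- Planned attrition: (203 − 143)/203 = 0.296, rounded to 30% (Protocol 2.7.3). It comes from the prior pneumonia project, whose last assessment was at 3 months (Protocol 2.2.3). The present study follows up at 1 month.
- Assumption: loss at M1 of 10% to 40%, because the documents give no one-month figure.

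**Case A: satisfaction not asked at M1.** The result depends on how Table 1 is read.
- Item by item: every row of the table requires baseline data to be present. Satisfaction has none, so no row applies and the M1 test has no data.
- Survey by survey: a participant reached by phone has an M1 survey, so nothing is filled and no M1 satisfaction value exists. A participant not reached receives the PT value. The M1 test then consists only of copied PT values from those not reached.
- Mixed (baseline judged by survey, M1 judged by item): every M1 value is a copy of PT, and the M1 test repeats the PT test.

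All three readings give the same conclusion: there are no one-month data, and whatever enters the M1 test is a PT rating.

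**Case B: satisfaction also asked at M1.** Participants reached contribute real M1 answers. Under the survey reading, those not reached receive their PT rating. The number copied per arm is 158 × loss, assuming all of them have PT data:
- 10% loss: 158 × 0.10 = 15.8, about 16
- 30% loss: 158 × 0.30 = 47.4, about 47
- 40% loss: 158 × 0.40 = 63.2, about 63

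Over both arms at 30%: 316 × 0.30 = 94.8, about 95. With equal loss c in the two arms, the filled M1 difference is (1 − c) × (M1 difference among those reached) + c × (PT difference among those not reached). At c = 0.30 the second term has weight 0.30. The direction of any distortion cannot be known from the documents.

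**PT missing (either case).** Table 1 directs the analyst to the baseline value. Neither document describes a baseline satisfaction item, and none could be meaningful. The fill is undefined for PT and, if M1 is also missing, for M1.

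**The case against.** The strongest reply is that satisfaction probably was asked at M1. The SAP is dated March 2020, is written in the past tense and describes comparisons already made at both times. Other plans had also moved on by then: SPSS to SAS, t-tests to Wilcoxon tests, and a survey of 5 to 10 items to two items. That is plausible, but the SAP does not say so, and the protocol's restriction to post-test was specific. The need to document the change stands.

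A second reply is that the SAP speaks of respondents, which may mean observed answers only. It may, but the Beliefs section uses the same word, again without an exemption from Table 1, so the word does not settle the denominator.

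A third is that few participants should lack PT data, because baseline and post-test are both given in person on the day of the session. This is fair: the number affected by the undefined baseline fill is probably small and cannot be sized from the documents. The 30% attrition may likewise be too high for M1, since the protocol chose one month partly because participants would be easier to reach; hence the range.

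A reader might also infer that percent favourable is inflated because unsure answers are left out. The documents do not support this. The satisfaction form is not shown, and the unsure option appears in a different instrument, the 2015 zoster survey in the Protocol Appendix. There, unsure answers are pooled with disagreement over all 58 responses.

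**Conclusion.** The protocol and SAP contradict each other on when satisfaction was measured, and the carry-forward rule as written is unsuitable for this outcome. If satisfaction was not asked at M1, the M1 test has no one-month data. If it was asked and Table 1 was applied by survey, about 47 of 158 M1 values per arm are same-day ratings at 30% loss, with a range of 16 to 63 for an assumed 10% to 40%. The baseline fill cannot be carried out in either case.

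A reader might go further and infer that every M1 satisfaction value is a copy of PT. That requires the post-test-only schedule to have been followed, Table 1 to have been applied to satisfaction, and the mixed reading of the table. The documents establish none of these, and the tense of the SAP points against the first.

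The point is minor. Satisfaction is the last objective, the SAP's Overview does not list it among the secondary measures, hypothesis 5 makes no one-month claim, and the primary knowledge analysis is unaffected.

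**What to change.** - State whether the two satisfaction items were asked in the one-month call.
- If they were not, delete the M1 satisfaction test.
- If they were, record the change from Protocol 2.7.2 with its reason, and analyse observed M1 responses only.
- In either case, exempt satisfaction from Table 1, analyse observed PT responses, and report the number answering in each arm at each time analysed.

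This needs a few sentences in the SAP and makes the analysis simpler. The cost is a somewhat smaller n for satisfaction: at M1, if the items were asked then, about 158 − 47 = 111 per arm at 30% loss, plus the loss of the few participants without a PT answer from the PT comparison.

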2.1 Objectives

- Compare the efficacy of PHARM vs. PEER at improving participant's knowledge regarding vaccine-preventable diseases
- Compare the efficacy of PHARM vs. PEER at improving participants' beliefs about vaccination
- 3) Measure the costs of PHARM and PEER from the senior center perspective
- 4) Compare the percent of participants taking activation step(s) to get vaccinated following receipt of PHARM vs. PEER
- 5) Determine the extent to which participants are satisfied with and trust the PHARM vs. PEER interventions

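### The satisfaction analysis pools Completely Agree with Somewhat Agree, so it cannot show whether either arm was highly satisfied, as Hypothesis 5 claims

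*SAP*

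**What the plan says.** Objective 5 (Protocol, 2.1 Objectives) is to "Determine the extent to which participants are satisfied with and trust the PHARM vs. PEER interventions". Hypothesis 5 (Protocol, 2.1.1 Hypotheses) is stronger: "Participants will be highly satisfied with the PHARM and PEER interventions". No numeric threshold is attached to either.

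Protocol 2.7.2, Satisfaction, names three domains: overall satisfaction with content and delivery, engagement, and satisfaction with the information given. On instrument and timing it says: "Satisfaction will be measured only at post-test using a simple 5-10 item satisfaction survey adapted from our prior research".

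The SAP's Satisfaction section covers "the two satisfaction items (program satisfaction and program engagement". At both post-test (PT) and one month (M1) it takes the proportion "answering favorably ('Completely Agree' or 'Somewhat Agree" and the corresponding pooled unfavorable proportion, and compares arms by Chi-Square or Fisher's Exact test. The SAP's Beliefs section, by contrast, counts *Completely Agree* alone. The SAP overview places randomization at the level of the program date and gives a carry-forward matrix for missing PT and M1 data. Trust, the other half of Objective 5, is listed there as a separate secondary measure.

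**The concern.** Hypothesis 5 is a statement about degree and about each arm's own level. The planned summary removes degree, because a participant who somewhat agrees and one who completely agrees are counted alike. Most satisfaction answers could well fall on the agree side. If they do, both arms will sit near the ceiling of the pooled measure and the only remaining contrast will be among the few who disagree. A report could then say that both programs were received equally well when one was received with clearly more enthusiasm.

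The second matter is scope. The protocol's information domain is not named in the SAP, and two items stand where 5-10 were planned, with no explanation. For an education program, what participants thought of the information is relevant to Objective 5.

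**Working it through.** The documents give no rate, margin, threshold or power for satisfaction, so there is no stated figure to reproduce.

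**1. What pooling loses, without any assumed rate.** Let C be the *Completely Agree* share, S the *Somewhat Agree* share, and F = C + S the favorable share.
- Within an arm, F only tells us that C lies between 0 and F. An arm in which everyone answers *Somewhat Agree* and an arm in which everyone answers *Completely Agree* both have F = 100%.
- Between arms, F1 - F2 = (C1 - C2) + (S1 - S2). A difference in C can be cancelled exactly by an opposite difference in S.

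**2. Illustration of an arm difference (assumed rates).** Take C = 75% vs 60% and S = 20% vs 35%, so F = 95% vs 95%. The pooled difference is zero by construction. For the top category, use a two-sided z test at 0.05 with 158 per arm (Protocol 2.7.3) and independence:
- mean proportion = (0.75 + 0.60)/2 = 0.675
- SE under no difference = sqrt(2 × 0.675 × 0.325/158) = 0.0527
- SE under the alternative = sqrt((0.75 × 0.25 + 0.60 × 0.40)/158) = 0.0520
- power = Φ((0.15 - 1.96 × 0.0527)/0.0520) = Φ(0.90) = 0.82

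With the protocol's 30% attrition, 158 × 0.70 ≈ 111 per arm and power is 0.67. That number is relevant to M1, since the post-test is on the day of the program. If the pooled shares differed slightly, at 95% vs 97%, power at 158 per arm would be only about 0.15.

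**3. Clustering.** PHARM is planned as 3 or 6 groups for 158 people, so about 53 or 27 per group (158/3 and 158/6, rounded up). Assume the same sizes for PEER and an intracluster correlation of 0.01 to 0.05; neither figure is in the documents. The design effect is 1 + (m - 1) × ICC.
- m = 27, ICC = 0.01: 1 + 26 × 0.01 = 1.26; effective n = 158/1.26 = 125; power 0.72
- m = 53, ICC = 0.05: 1 + 52 × 0.05 = 3.60; effective n = 158/3.60 = 44; power 0.32

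The 0.82 is therefore an upper figure for that example.

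**4. Items and timing, side by side.**

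| | Protocol 2.7.2 | SAP, Satisfaction |
|---|---|---|
| Items | 5-10 | 2 |
| Domains named | overall; engagement; information | program satisfaction; engagement |
| Timepoints | post-test only | PT and M1 |

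**5. Carry-forward.** The SAP matrix fills a missing PT value from baseline, and fills both PT and M1 from baseline when both are missing. Nobody can rate a program before attending it, so no baseline value exists. The SAP does not exempt satisfaction from the matrix.

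**The case against.** Much of the case on the other side stands.

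- A reader might infer that Objective 5 cannot be answered. It asks for the extent of satisfaction and trust, framed as PHARM vs PEER, and does not contain the word *highly*. A between-arm comparison addresses it, and trust is a separate SAP measure.
- A reader might infer that the SAP treats *Somewhat Agree* as success. It does not: it speaks of favorable answers, sets no success criterion, and nowhere says that a favorable share supports Hypothesis 5.
- A reader might infer that an arm comparison says nothing about level. Comparing two proportions means computing each, so each arm's favorable share is available. Only the split within agreement is lost.
- A reader might infer that items were collected and then dropped, with 20-40% of them analysed. The SAP's wording can equally mean that two items were all that was fielded. The wording of the program satisfaction item is not shown, and overall satisfaction with content may overlap with satisfaction with information.
- The power figures rest on assumed rates. Pooling is not always the worse choice: if arms differed mainly in how many disagreed, the pooled share would be the more sensitive summary.

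None of this restores the distinction between highly and somewhat satisfied, and the SAP does not say why satisfaction has a looser cut-off than beliefs.

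**Conclusion.** The point holds in a limited form. As written, the SAP yields no result that bears on *highly* in Hypothesis 5, and it discards information about an arm difference in degree. The first part follows from the definitions and needs no assumption. The size of the second is unknown: it depends on the response distribution and on correlation within program dates, and the range of 0.32 to 0.82 describes one assumed example only.

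The satisfaction component of Objective 5 is answered at most in part; it is not unanswerable. Whether the information domain was never asked or was asked and not analysed cannot be settled from the documents. The timepoints in protocol and SAP disagree, and the baseline carry-forward cannot apply to this outcome. This is a secondary objective; the primary knowledge comparison and its sample size are not touched.

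**What to change.** 1. For each satisfaction item, report the full response distribution and the *Completely Agree* share per arm, with 95% confidence intervals that allow for clustering by program date. With few dates per arm these may be wide, and the report should say so.
2. Compare arms on the ordered response, again allowing for program date, and keep the pooled favorable share as a secondary summary. State where any neutral or unsure answer is placed; the SAP's two groups leave no room for one, and the 2015 member survey in the protocol appendix offered such an option.
3. Analyse any further satisfaction items that were collected. If only two were fielded, say so and limit the Objective 5 satisfaction conclusion to program satisfaction and engagement.
4. Reconcile the protocol's post-test-only measurement with the SAP's use of PT and M1.
5. Exclude satisfaction from baseline carry-forward and state how missing answers are handled.

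The cost is SAP wording and a few more table rows from responses already recorded by category. The headline percentage will be no higher than the pooled one, and usually lower. A domain that was never asked about cannot be recovered. Because the SAP is written in the past tense, the additions should be labelled as such in the report.
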